#### **Study Design:**

This is an unblinded pilot study enrolling women with C1 catamenial focal epilepsy. Subjects will chart menses and seizures for a 2 month baseline period and then be randomized into 2 parallel arms: (1) Fycompa 4 mg daily and (2) Fycompa 4 mg daily to be increased to 6 mg daily peri-menstrually (Day -7 until Day 4 of menstruation where Day 1 is the first day of menstrual flow). During this treatment phase, subjects will continue to chart menses and seizures. Other anticonvulsant medication doses will not be changed during the baseline or treatment study period.

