#### **Objectives:**

*Primary*: To determine the responder rate in each group (percent of patients experiencing a 50% or greater reduction in seizures) relative to baseline seizure frequencies.

Secondary: Changes in seizure frequency in each group relative to baseline seizure frequencies.

Tertiary: Comparisons of primary and secondary outcomes between two groups.

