#### **Inclusion Criteria:**

- 1. Female
- 2. Diagnosis of focal onset seizures (FOS)
  - i. Established by clinical history and an EEG
  - ii. Patients with a normal EEG may be included if they met other diagnostic criteria based on clinical history
- 3. Presumably ovulatory women based on menstrual cycles of 21-35 days from beginning of menstrual flow to the beginning of the next menses
- 4.  $\geq$ 18-50 years old
- 5. ≥2 unprovoked seizures per month despite drug trials with ≥1 first-line antiepileptic drugs (AED)
- 6. Seizures must show a C1 catamenial pattern in 2 of 3 documented cycles
  - i. C1 pattern will be defined as a two-fold increase in average daily seizure frequency during the menstrual phase, as compared to the follicular and luteal phases of the ovulation cycle, in 2 of 3 documented cycles. The menstrual phase will be defined as days -3 to +3 of the menstrual cycle (where onset of menstruation is defined as day 1) (Herzog et al, 1997). Of note, in the NIH Progesterone Trial, the level of catameniality was 1.69 based on Herzog et al. (1997) criteria though this trial will use a level of 2 to include women only with high levels of perimenstrual catamenial exacerbation.
- 7. Willingness and ability to comply with scheduled visits and study procedures

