#### **Safety Measures:**

- 1. We do not plan to have an internal Data Safety Monitoring Board. PI and study coordinator to be in charge of safety measures.
- 2. There will be a baseline Columbia-Suicide Severity Rating Scale (C-SSRS) at enrollment to screen for suicidal ideation and behaviors. If suicidal ideation or behaviors are present, subjects will not be enrolled in the study. At each followup visit, we will screen for changes in this scale. During each telephone call, we will screen for depressive symptoms and suicidality by asking patients if they are suicidal.
  - 1. Suicidality plan:
    - a. C-SSRS will be performed at each visit by study coordinator. Study coordinator to contact PI if there is a change in the C-SSRS.
    - b. For suicidal ideation and/or behaviors, we will refer subject to the Emergency Department for emergent evaluation and treatment. Phone number for suicide hotline will also be provided. Will also discontinue enrollment in trial and study drug.
- 3. We will screen for behavioral changes at each visit and during each telephone call.
  - 1. Will screen by asking specifically if patient is having:
    - a. Thoughts of harming others, physical assault, or threating behavior
    - b. Worsening anger, aggression, or irritability

- 2. If thoughts of harming others, physical assault, or threating behavior develops in a subject, will discontinue enrollment in trial and study drug. Subject will be referred to the Emergency Department.
- 3. If worsening anger, aggression, or irritability is mild or moderate, will continue enrollment and continue monitoring subject.
- 4. If worsening anger, aggression, or irritability is severe, will discontinue enrollment in trial and study drug.
- 4. We will check a serum pregnancy prior to enrollment in baseline phase and then a urine pregnancy test prior to enrollment in treatment phase to ensure pregnant women are excluded.
- 5. Subjects who are not status post tubal ligation or who do not have an IUD must agree to use a double barrier contraceptive method while enrolled in study (e.g. condom + spermicide OR condom + diaphragm/cervical cap).
  - a. During monthly telephone calls while enrolled in the study (see "Data Collection" below), subjects will be reminded to utilize the double barrier contraceptive method while enrolled in the study.

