# **Correlative Science:** N/A

# **Statistical Analysis:** The primary outcome (50% responder rate) will be analyzed using Chi square analysis. The secondary outcome, changes in seizure frequency from baseline to treatment, will be analyzed using paired t-test or ANCOVA.

The pilot should provide data for calculation of the required sample size for demonstration of a significant difference or equivalence between the two groups with 80% power.

Data Collection:	Subjects will be seen in the clinical trial clinic for three separate visits. Subjects will be seen at enrollment and then also after the completion of baseline (first 2 months of charting) and treatment phases (second 2 months of charting). Subjects will also be contacted by phone on a monthly basis to verify compliance with charting and treatment and to monitor for any adverse effects. [Subjects will also be reminded to utilize double barrier contraceptive methods during these phone calls]. Data will be obtained via paper charting on printed calendar and then entered into an electronic database (REDCap) for analysis. All adverse events will be reported to the IRB.
Study Drug Regimens:	During the treatment phase, subjects will be randomized into 2 parallel arms: (1) Fycompa 4 mg daily and (2) Fycompa 4 mg daily to be increased to 6 mg (4-mg pill and 2 mg pill) daily peri-menstrually (from Day -7 until Day 4 of menstruation where Day 1 is the first day of menstrual flow). This treatment phase will last for two menstrual cycles.
Study Drug Requested Per Patient:	Group 1 (n=25), to take 4 mg daily for 2 menstrual cycles or 60 days, 1500 tablets (25 subjects x 60 days).
	Group 2 (n=25), to take 4 mg daily (1 tablet) with 6 mg daily (1 4-mg tablet and 1 2-mg tablet) for 11 days around menses for 60 days. This would be 1500 tablets (25 subjects x 60 days) of 4 mg tablets and 550 tablets (25 subject x 22 days) of 2 mg tablets.

Are Clinical/Drug Supplies Requested? (check only 1 box): D YES' ('YES') 'NO'

Total study drug amount in units (tablets, capsules, vials, etc.):		
Total Active Drug	3000 tablets of 4 mg tablets needed	
	550 tablets of 2 mg tablets needed	
Amount of Pure Substance		
(if applicable)		

Estimated Length of Enrollment:

I plan to enroll 50 patients within a 6 month time period.

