Title: Pilot Study of Add-On Fycompa (perampanel) Treatment for Catamenial Epilepsy

NCT number: NCT05201703

Date of document: 3/17/2022

Statistical analysis plan:

The primary outcome (50% responder rate) will be analyzed using Chi square analysis. The secondary outcome, changes in seizure frequency from baseline to treatment, will be analyzed using paired t-test or ANCOVA. The pilot should provide data for calculation of the required sample size for demonstration of a significant difference or equivalence between the two groups with 80% power.

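### All three safety stops end trial participation along with study drug, so later data are lost, and no rule says how a stopped woman counts in the responder rate

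*Protocol*

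**What the plan says.** The Protocol's Safety Measures section contains three stop rules.

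- Suicidal ideation or behavior (item 2, plan b): "Will also discontinue enrollment in trial and study drug".
- Thoughts of harming others, assault or threats (item 3, sub-item 2): "will discontinue enrollment in trial and study drug. Subject will be referred to the Emergency Department".
- Severe behavioral change (item 3, sub-item 4): "If worsening anger, aggression, or irritability is severe, will discontinue enrollment in trial and study drug".

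By contrast, a woman with mild or moderate anger or irritability stays enrolled and monitored (item 3, sub-item 3).

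Data Collection lists the only planned contacts: visits at enrollment, after baseline and after treatment, plus monthly calls. Seizures are recorded on the woman's own paper calendar. On the length of treatment, Study Drug Regimens says "This treatment phase will last for two menstrual cycles".

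The primary outcome is the "percent of patients experiencing a 50% or greater reduction in seizures", relative to baseline frequencies. The SAP says of it only this: "The primary outcome (50% responder rate) will be analyzed using Chi square analysis". Neither document defines an analysis set, a missing-data rule, a minimum chart length or the handling of a partial treatment period.

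**The concern.** Stopping a drug for safety and ending follow-up are separate decisions, and the three rules make them together. A missing table can be built later from data on file, but seizures and C-SSRS scores that were never recorded cannot be recovered.

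A percentage of patients also needs a denominator, and a stopped woman has to be put somewhere. Study Design says "This is an unblinded pilot study enrolling women with C1 catamenial focal epilepsy", so without a written rule that choice can be made with arm and outcome known. The arms differ in perimenstrual dose (4 mg or 6 mg), so stops could differ by arm. The SAP wants the pilot's data to size a later two-group trial, and the counting choice feeds into that.

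**Working it through.** **1. Text.** The plan states no stop rate, dropout allowance or derivation of the 50 women, so it has no figure to reproduce. That charting ends after a stop is an inference. It rests on the wording (enrollment ends), on the contrast with mild or moderate cases (enrollment and monitoring continue), and on the absence of any post-stop contact.

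**2. What one woman is worth.** Each arm has 25 women (Study Drug Requested Per Patient), so one woman is 1/25 = 4 points. Assume 10 responders among the women not stopped, and *s* stops. The three counting rules give 10/25 (non-responder), 10/(25 − s) (left out) and at most (10 + s)/25 (every short chart scored as a response).

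| Stops | Non-responder | Left out | Upper bound, short charts |
|---|---|---|---|
| 1 | 40.0% | 41.7% | 44.0% |
| 3 | 40.0% | 45.5% | 52.0% |
| 5 | 40.0% | 50.0% | 60.0% |

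**3. Effect on sizing the next trial.** Assume two-sided 5% alpha with the plan's 80% power. Size per arm = (1.960 + 0.842)² × [p1(1 − p1) + p2(1 − p2)] / (p1 − p2)².

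- One stop in each arm, with 10 of 24 and 14 of 24 responding: 0.400 vs 0.560 gives 149 (non-responder); 0.417 vs 0.583 gives 137 (left out); 0.440 vs 0.600 gives 149 (upper bound).
- One and three stops, with 10 of 24 and 13 of 22 responding: 0.400 vs 0.520 gives 267; 0.417 vs 0.591 gives 125; 0.440 vs 0.640 gives 94.

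The rule hardly matters when stops are few and equal, and matters when they differ. The stop numbers are assumptions.

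**4. How far a short chart misleads.** Simulation of 400,000 women per setting with no drug effect: 28-day cycle, six menstrual-phase days at twice the daily rate of other days, Poisson counts, and treatment starting on a random cycle day. Baseline is 56 days with at least 4 seizures (entry requires at least 2 per month). A responder has a daily rate at least 50% below baseline.

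| Mean seizures per two cycles | Full 56-day chart | 28-day chart |
|---|---|---|
| 4 | 33.2% | 43.0% |
| 8 | 11.8% | 20.0% |
| 12 | 6.3% | 13.0% |

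Day 28 is the relevant length because the monthly call is the only planned contact between the start and end of treatment.

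**5. Is the catamenial pattern the cause?** Entry requires a "two-fold increase in average daily seizure frequency during the menstrual phase". The simulation was repeated with that pattern removed (equal rate on all days).

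| Mean seizures | 14 days, two-fold | 14 days, flat | 7 days, two-fold | 7 days, flat |
|---|---|---|---|---|
| 4 | 40.5% | 40.1% | 61.1% | 60.7% |
| 8 | 29.8% | 29.4% | 38.0% | 37.1% |
| 12 | 23.0% | 22.1% | 28.9% | 27.6% |

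The pattern adds 0.4 to 1.3 points. At 28 days it adds nothing, because any 28-day window holds one whole cycle. The excess comes from small counts.

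**The case against.** The case against has several sound parts.

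- **Pilot status.** The primary objective is a rate within each group, and the between-group comparison is only tertiary. For 0.400 vs 0.520 at 25 per arm, the 95% interval is 0.12 ± 1.96 × √(0.2400/25 + 0.2496/25) = 0.12 ± 0.27, or about −15 to +39 points. The three rules in that example give differences of 12, 17 and 20 points, so sampling error is larger than the choice of rule. This stands and limits the consequence, but a descriptive rate still needs a denominator.
- **Post-stop charting cannot alter the primary result if stoppers are non-responders.** True. It serves the supporting rate, the secondary outcome and safety.
- **Any dropout raises the counting question.** Also true. Safety stops are the case in which the plan itself ends data collection.

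A reader might infer four stronger things that the documents do not support.

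- *Short charts mislead because they miss the menstrual phase.* A 14-day chart misses it for 9 of 28 start days (32%), but step 5 shows that this contributes about one point.
- *A half-length chart halves the count and creates responders.* Scored by raw count, 55% to 75% of null 28-day charts would look like responses. But response is defined relative to baseline seizure frequencies, so a rate is the natural reading.
- *The next trial's size is distorted several-fold.* That needs assumed, unequal stops. The upper-bound column also scores every short chart as a response, whereas the simulation gives about 20% at 28 days with 8 seizures.
- *Stopped women are left without care.* Perampanel is add-on, other anticonvulsant doses stay unchanged, and two of the three rules refer to the Emergency Department. Only planned trial monitoring ends.

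**Conclusion.** The concern holds in a limited form. Following the three stop rules as written loses outcome and safety data that cannot be recovered, and the place of these women in the responder rate is undefined. Each is worth up to 4 points in an arm of 25. The total effect on the pilot's estimates is unknown because no stop rate is given, and it is small if stops are few and balanced. Scoring a 28-day chart by daily rate raises the false-responder share from about 12% to 20% at 8 seizures per two cycles, under a Poisson model with no drug effect. The conclusion also rests on reading the end of enrollment as the end of charting and contact, which the text implies but does not state. This is a cheap improvement worth making; it does not undermine the trial.

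**What to change.** **Protocol, Safety Measures (the three rules).** Replace the phrase that ends both enrollment and drug with: *stop study drug; unless she withdraws consent, she keeps charting and keeps the monthly calls and the final visit with C-SSRS to the end of her planned two cycles.*

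**SAP.** Add: *The denominator is all randomized women. A woman who stops study drug early is a non-responder. Her response based on the rate over the full charted period is given as a supporting result. The secondary outcome is scored per day over the full charted period.* The investigator may prefer another counting rule, provided that it is written before outcomes are seen.

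**Cost.** One phrase in three places, a few SAP sentences and possibly a line of consent text. The calendar, calls and final visit are already planned for every woman, and drug is stopped exactly as now. The downsides are slight extra follow-up of the women who stop and some off-drug days in the secondary outcome.

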# **Adverse Events:**

- 1. Serious FDA definition: A serious adverse event results in death, is lifethreatening, requires inpatient hospitalization or prolongation of existing hospitalization, results in persistent or significant disability / incapacity, results in a congenital anomaly / birth defect.
- 2. Severity: Severity describes the intensity of a specific event and will be graded as:
  - a. Mild: easily tolerated, causing minimal discomfort.
  - b. Moderate: sufficiently discomforting to interfere with every day activities.
  - c. Severe: prevents normal every day activities.
- 3. Relationship will be detailed as:
  - a. Unrelated: There is no association between the study intervention and the reported event.
  - b. Related: A definite causal relationship exists between the event and the study, and other conditions (concurrent illness, progression of disease or concomitant medication use do not appear to explain the event).
  - c. Cannot be ruled out: The event might be related to the intervention, but could also have been produced by other factors.

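### Both pregnancy tests come before the first dose, and the available text ties no test, drug decision or follow-up to a late period or pregnancy during about 60 days on perampanel

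*Protocol*

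**What the plan says.** Safety Measures item 4 of the protocol schedules a serum pregnancy test before the baseline phase and "a urine pregnancy test prior to enrollment in treatment phase to ensure pregnant women are excluded". Under Study Design, perampanel is given only after the 2-month baseline, so both tests precede the first dose. Study Drug Regimens sets treatment at two menstrual cycles, and the drug request equates this with 60 days. Eligible women have "menstrual cycles of 21-35 days from beginning of menstrual flow to the beginning of the next menses" (Inclusion Criteria, item 3).

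Several safeguards operate during treatment:

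- Women without a tubal ligation or IUD "must agree to use a double barrier contraceptive method while enrolled in study", and the monthly calls repeat the reminder (Safety Measures, item 5).
- The calendar continues: "During this treatment phase, subjects will continue to chart menses and seizures" (Study Design).
- Subjects are "contacted by phone on a monthly basis to verify compliance with charting and treatment and to monitor for any adverse effects" (Data Collection).
- Adverse events go to the IRB (Data Collection), and an event is serious if, among other things, it "results in a congenital anomaly / birth defect" (Adverse Events, item 1).

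Pregnancy is an entry exclusion (Exclusion Criteria, item 3). Safety Measures also writes an explicit on-treatment stop for suicidality, "Will also discontinue enrollment in trial and study drug", and similar stops for threatened harm to others and for severe anger or irritability. The SAP does not mention pregnancy.

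**The concern.** Item 4 gives its own purpose, which is to keep pregnant women out. The checks that serve that purpose end when exposure begins. The trial selects presumably ovulatory women aged 18 to 50 and excludes recent systemic hormonal contraception, so a pregnancy on treatment is foreseeable. There is no internal safety board; the investigator and coordinator carry safety between them, which makes a written trigger more useful.

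If a woman conceives in her first treatment cycle, her late period will be on the calendar, but nobody is told to act on it. Nothing says whether she continues drug, who is informed, or whether the pregnancy is followed. The birth-defect category only classifies an outcome that someone has learned of. The last scheduled visit comes at the end of treatment, so a birth would fall after all planned contact. At stake is avoidable exposure and a lost pregnancy outcome.

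**Working it through.** **The plan's own figures.** The drug request gives 25 × 60 = 1500 tablets of 4 mg per arm and 1500 + 1500 = 3000 in all. The 6 mg step runs from Day −7 to Day −1 (7 days) plus Days 1 to 4 (4 days), which is 11 days per cycle. Over two cycles that is 22 days, and 25 × 22 = 550 tablets of 2 mg. All of these match the protocol, so 60 days is the planned exposure. Two cycles at the eligible lengths run from 2 × 21 = 42 to 2 × 35 = 70 days.

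**Tests after the first dose.** 0 of 2.

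**Exposure after a missed period.** Let L be the cycle length. Assume that treatment day 1 is cycle day 1; the documents do not fix this. After a first-cycle conception:

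- Missed menses is due on day L + 1.
- A rule of 7 days late acts on day L + 8.
- Dosing days left are 60 minus that day.

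| | L = 21 | L = 28 | L = 35 |
|---|---|---|---|
| Menses due (L + 1) | 22 | 29 | 36 |
| Days left of 60 from due date | 38 | 31 | 24 |
| Trigger day (L + 8) | 29 | 36 | 43 |
| Days left of 60 from trigger | 31 | 24 | 17 |
| Days left from trigger if dosing ends at 2L | 42 − 29 = 13 | 56 − 36 = 20 | 70 − 43 = 27 |

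**Second-cycle conception.** Menses is due on day 2L + 1 = 43, 57 or 71, leaving 17, 3 or 0 of the 60 days. The gap in drug decisions therefore mainly concerns the first cycle. The gap in follow-up concerns both.

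**Start day.** If treatment starts on cycle day k, the first due date and the trigger both come k − 1 days earlier, and k − 1 more dosing days remain. With L = 28 and k = 15, the trigger is day 36 − 14 = 22, leaving 60 − 22 = 38 days. For the cycle in progress, starting on day 1 is thus the assumption that leaves the fewest days.

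**Would the calls alone do?** Assume calls on days 30 and 60. A 21-day cycle reaches its trigger on day 29 and is caught on day 30. Cycles of 28 and 35 days reach theirs on days 36 and 43, so they are caught only on day 60, with no dosing left. Subjects therefore also need an instruction to phone in.

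**The case against.** The strongest reply is that the existing controls form a working net. Contraception is mandatory and repeated monthly. The calls verify charting, and the chart includes menses, so staff have a route to an absent period. The investigator is in charge of safety and would presumably act. This is a pilot with 50 women and about two months of drug. Those points bear on weight: they make a pregnancy less likely and detection more likely. They do not supply a test, an action or follow-up, and the same section writes such actions for other hazards.

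Three stronger readings are tempting, but the documents do not support them:

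- A reader might infer that the plan keeps pregnant women on drug. The text neither directs nor rules that out.
- A reader might infer likely fetal harm. The documents give no fetal-risk information for perampanel and no conception rate, so only dosing days can be counted.
- A reader might infer that the trial has no pregnancy procedure anywhere. Consent pages, some other pages and the schema figure are not available, and a procedure could sit there.

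A fourth temptation is to cap the arm 2 step at 11 days because its end is anchored to menses. The supply figure shows that 11 days is the planned length, but a cap could work against the design. If the step starts 7 days before expected menses and menses comes 5 days late, day 11 of the step is actual Day −2. Only Days −3 and −2 would be covered, 2 of the 6 days (−3 to +3, no day 0) that the inclusion criteria define as the menstrual phase. No such cap is proposed.

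**Conclusion.** The point holds for the available text: no pregnancy test is scheduled after the first dose, and a late period or a pregnancy on treatment prompts no written test, drug decision or follow-up. For a first-cycle conception, a 7-day rule would open 31, 24 or 17 of 60 dosing days to an investigator decision for cycles of 21, 28 or 35 days. This rests on treatment starting on cycle day 1, dosing lasting 60 days, and subjects phoning in when late. The gap should be corrected for subject safety. It does not bear on the responder or seizure-frequency analyses. Confidence is medium because the missing pages and schema cannot be checked.

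**What to change.** Add to Safety Measures item 4:

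- **Trigger.** At each treatment-phase call, the coordinator asks whether the expected menses arrived. Subjects are told to phone between calls if it is 7 days past the expected date. Either route leads to a urine pregnancy test and notice to the investigator. Count lateness from each woman's own expected date: a fixed limit at cycle day 35 would flag a woman with a 35-day cycle on day 36, the day her period is due.
- **Final test.** Do a urine pregnancy test at the existing end-of-treatment visit and at any early stop.
- **Positive test.** Study participation ends. The investigator decides individually whether and how perampanel is tapered or stopped. The pregnancy is reported to the IRB and followed to outcome.

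The cost is protocol wording, one question per existing call, about 50 urine tests at a visit already planned, and a few follow-up contacts if a pregnancy occurs. Some late cycles will give negative tests. Stopping an add-on anticonvulsant may carry seizure risk in women who enter with at least two "unprovoked seizures per month despite drug trials with" at least one first-line drug, so the decision to stop is left to the investigator. The final-visit test comes after exposure and can miss the latest conceptions, so the late-menses trigger does most of the work.
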